## **AIMS**

ICD-11 CPTSD is a new condition and there are currently no identified effective treatments to enable recovery from this debilitating condition. Identifying effective interventions to treat veterans with CPTSD is therefore of paramount importance. We have recently proposed in the research literature a new innovative person-centred treatment approach for CPTSD (i.e. modular therapy; Karatzias and Cloitre, 2020). Enhanced Skills Training in Affective and Interpersonal Regulation (ESTAIR) involves targeting the symptoms of CPTSD clusters sequentially using concrete modules (i.e. specific number of sessions targeting specific clusters of symptoms). This intervention has never been tested in a military population before.

The project will provide information on recruitment and acceptability of a new treatment for CPTSD. The following main research questions will be addressed as part of this pilot project:

- I. Is it feasible to recruit for a study on ESTAIR vs. TAU in military personnel during the study recruitment period?
- II. What is the retention rate in the study at the end of treatment and at 3-month follow-up?
- III. Are primary and secondary outcomes acceptable from participants?
- IV. Is the new ESTAIR protocol acceptable by people with CPTSD?

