## **STUDY DESIGN**

To our knowledge, this is the first pilot trial in the world on the acceptability of modular therapy for veterans with CPTSD using a new treatment manual. The present study has been approved by Edinburgh Napier University (SHSC2686062).

A randomised trial design will be employed, adhering to the *Consolidated Standards of Reporting Trials* (CONSORT; Schulz, 2010). This study has been designed to confirm that we can successfully recruit and retain participants in a larger trial characterised by the same design parameters (e.g., allocation ratio, blind assessment, types of treatment and control

offered, multiple sites). The planned randomised pilot study is therefore a 28-month feasibility/pilot of a single site, single (rater) blind trial of ESTAIR (psychological intervention vs. treatment as usual (TAU) alone for the treatment of CPTSD using the ITQ as the primary outcome. In this study, participants will be randomly allocated to receive treatment as usual (TAU) or a psychological intervention (ESTAIR) to improve CPTSD symptoms.

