## **STATISTICAL CONSIDERATIONS**

### **Sample size**

There are currently no effectiveness studies on the psychological interventions for CPTSD to enable power calculations. Following a pragmatic approach and in line with previous pilot studies in the area of PTSD we will aim to recruit  $n=30$  individuals per arm (total sample = 60). This approach will enable us calculating sample size for an adequately powered trial.

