### **Data analysis**

#### ***Recruitment and Retention***

Recruitment and retention rates at all stages of the trial will be recorded and summarised as counts and percentages.

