Phase 2: The primary intention to treat analysis will be conducted to examine differences between the ESTAIR and TAU groups at 25 weeks. This analysis will be conducted using a regression approach, simultaneously regressing the 25 week mean scores of the ITQ, PHQ-9, GAD-7, PHQ-15, and AUDIT onto a dummy-coded binary variable representing the treatment and control group (ESTAIR = 1, TAU = 0). The estimated regression coefficient for each variable indicates the mean difference between the treatment and control group, and the associated  $p$ -values indicate statistical significance. This approach was used as (1) all the model parameters are estimated simultaneously thereby avoiding the need for post-hoc adjustment for multiple testing, (2) the use of robust maximum likelihood (MLR) estimation allows for missing data to be handled efficiently by using all available data (Schafer & Graham, 2002), and third, MLR estimation is robust against deviations from normality and produces unbiased standard errors (West, Finch, & Curran, 1995). Furthermore, the

standardised regression coefficients from this model can be used as a useful analogue to Cohen's *d* as a measure of effect size (Nieminen, Lehtiniemi, Vähäkangas, Huusko, & Rautio, 2013): *d*=0.20 is a 'small' effect, *d*=0.50 is a 'medium' effect, and *d*=0.80 is 'large' effect size.

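### Recruitment and retention are to be reported without intervals, while efficacy, which is not a research question and was not powered, is the main and primary analysis and is read from p-values

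*Combined protocol and SAP*

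**What the plan says.** All references are to the combined protocol and SAP.

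- **Purpose.** Aims lists four main questions: recruitment (I), retention (II), acceptability of the outcome measures (III) and acceptability of ESTAIR (IV). Question II reads "What is the retention rate in the study at the end of treatment and at 3-month follow-up". Study Design states "This study has been designed to confirm that we can successfully recruit and retain participants in a larger trial", and also describes the trial as "using the ITQ as the primary outcome". No question asks whether ESTAIR works.
- **Sample size.** 30 per arm, 60 in total, on pragmatic grounds: "There are currently no effectiveness studies on the psychological interventions for CPTSD to enable power calculations". The aim is forward-looking: "This approach will enable us calculating sample size for an adequately powered trial".
- **Feasibility analysis.** The whole of Recruitment and Retention is "Recruitment and retention rates at all stages of the trial will be recorded and summarised as counts and percentages". Acceptability is handled separately, by thematic analysis (Qualitative analyses).
- **Score analysis.** Quantitative analyses calls its two phases the main analyses. Phase 1 tests within-arm ITQ change with a chi-square comparison of models, then pairwise Wald tests. Phase 2 is named the primary intention-to-treat analysis. It regresses five 25-week scores on arm, and the p-"values indicate statistical significance". Both phases add standardised effect sizes, without intervals. Neither is labelled exploratory.
- **Progression.** Progression Criteria for a Full Trial requires target recruitment and 25-week ITQ data from at least 75% of those randomised.

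**The concern.** The weight of the analysis does not match the purpose of the study. The words main and primary are attached to a question that the pilot does not ask and was not sized for. The two quantitative questions that it does ask get point figures with no statement of precision.

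Two things are at stake. First, the pilot is meant to supply the inputs for sizing a full trial. At 30 per arm, a between-arm difference singled out because it reached significance will tend to be too large unless the true effect is large, and a full trial sized on it will be too small. A non-significant difference says little about a small or medium effect. Second, a retention percentage quoted alone, beside a 75% threshold, looks firmer than 60 participants can make it.

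**Working it through.** **Inputs.** From the plan: 30 per arm; a 75% threshold, so 0.75 × 60 = 45 with 25-week data; benchmarks d = 0.2, 0.5 and 0.8 (Phase 2); a regression on arm alone, with no baseline covariate. Assumed, because the plan does not state them: two-sided 5%, SD = 1, and losses split evenly between arms (22.5 per arm). The plan gives no expected effect, so its three benchmarks serve as the range. It states no power that could be reproduced.

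**Smallest significant difference.** SE = √(2/n) and critical d = t(0.975; 2n−2) × SE.

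- n = 30: SE = 0.258; 2.002 × 0.258 = 0.52.
- n = 22.5: SE = 0.298; 2.017 × 0.298 = 0.60.

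**Power and overstatement.** Power is from the noncentral t with noncentrality d/SE. Overstatement is the mean absolute estimate among significant results divided by the true d, treating the estimate as normal. Worked case, d = 0.5 and n = 30: (0.517 − 0.5)/0.258 = 0.065; upper-tail probability 0.474; normal density 0.398; mean = 0.5 + 0.258 × 0.398/0.474 = 0.717; ratio 1.43. The opposite tail is negligible here and is included below.

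| True d | Power, 60 analysed | Power, 45 analysed | Overstatement, 60 | Overstatement, 45 |
|---|---|---|---|---|
| 0.2 | 12% | 10% | 3.2× | 3.7× |
| 0.5 | 48% | 37.5% | 1.43× | 1.61× |
| 0.8 | 86% | 75% | 1.08× | 1.16× |

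Normal critical values, closer to the plan's likelihood-based estimation, change little: 49% and 39% power at d = 0.5.

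**Effect on full-trial size.** For 80% power, n per arm = 2 × (1.960 + 0.842)²/d² = 15.70/d². At d = 0.5 this is 62.8, so 63 per arm. The mean significant estimates at a true 0.5 are 0.72 and 0.81, and they give 15.70/0.72² = 30.3 and 15.70/0.81² = 23.9, so about 31 or 24 per arm. The first is about the pilot's own size, where power at d = 0.5 is 48%.

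**What intervals would show.** The 95% half-width for d is 1.96 × SE: 0.51 with 60 analysed and 0.58 with 45. The pooled SD, which full-trial sizing also needs, has a 95% interval of 0.85 to 1.22 times its estimate (60) or 0.83 to 1.27 times (45).

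**Retention.** Exact (Clopper-Pearson) 95% intervals: 45/60 = 75%, 62% to 85%; 48/60 = 80%, 68% to 89%; one arm at 24/30 = 80%, 61% to 92%. Binomial probability of at least 45 of 60:

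- true retention 70%: 24%
- true retention 75%: 57%, so missed 43% of the time
- true retention 80%: 87%

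**The case against.** The strongest reply is that no decision depends on a p-value. Progression rests on recruitment and data completeness, so a non-significant difference blocks nothing. That stands, and it limits the harm to reporting and planning. A reader might infer that a null result would count against ESTAIR. The plan does not say so, although nothing in it guards against that reading.

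Other stronger readings are tempting and also fail:

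- *Any significant estimate must be inflated.* This is true only when the true effect is below the critical value of 0.52 or 0.60. At d = 0.8 a significant estimate can fall below the truth, and average overstatement is 8% to 16%.
- *All the pilot's questions get bare percentages.* Only I and II do. Acceptability has its own data collection, thematic analysis and the added Friends and Family Test.
- *Efficacy is judged by p-values alone.* Effect sizes are planned in both phases. They lack intervals.
- *The plan admits that it is underpowered.* It says only that no studies existed on which to base a power calculation.

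It can also be said that a 95% interval carries the same test as a two-sided 5% p-value, and that a point threshold is a legitimate decision rule. Both are correct. The interval still shows which effects remain compatible with the data, and the 75% rule need not change to be reported with its precision.

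**Conclusion.** The point holds as a mismatch between purpose and analysis that should be corrected. The quantitative feasibility questions have no measure of uncertainty, while an unpowered efficacy comparison carries the titles main and primary and is read for significance.

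The size depends on the unknown true effect. The problem is serious at d = 0.2 and material at d = 0.5, where a non-significant result has probability 52% to 62.5%. It is mild at d = 0.8. These figures rest on the assumed two-sided 5% level, an unadjusted comparison, and 45 to 60 analysed. The retention intervals need none of the test assumptions, only independent participants. The go/no-go decision is not driven by the efficacy tests.

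**What to change.** 1. **Recruitment and Retention:** make recruitment, 25-week and follow-up retention, and data completion the main analysis. Give exact 95% intervals for retention and completion, with those randomised as denominator, overall and by arm. Give an exact interval for the proportion of eligible veterans approached who are randomised, and a Poisson interval for the 12-month recruitment rate.
2. **Quantitative analyses, Phases 1 and 2:** label both exploratory. Replace the significance wording, including that for the Phase 1 chi-square and Wald tests, with estimates, SDs and 95% intervals. State that no efficacy conclusion will be drawn.
3. **Progression Criteria:** keep the 75% rule and report the retention interval beside the decision.

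This costs rewording and a few extra intervals, with no new data, participants or visits. The downside is that the report will have no headline p-values.

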## OUTCOME MEASURES

Outcomes are as follows: **(i)** Retention & data completion rates at weeks 25 weeks post-treatment and 12-week follow-up, on the primary outcome; International Trauma Questionnaire (Cloitre et al., 2018) and secondary outcomes: PHQ Depression (Kroenke et al., 2001), GAD Generalised Anxiety (Spitzer et al., 2006), AUDIT Substance Misuse (Saunders et al., 1993), and PHQ-15 Medically Unexplained Symptoms (Kroenke et al., 2002) **(ii)** 12-month recruitment rate; **(iii)** participant & clinical staff views on trial & intervention acceptability and suggested changes. Baseline information on demographics including age, gender, marital status etc., will be gathered to characterise the sample.

A range of assessments will be administered by the research assistant to test the acceptability of primary (PTSD and CPTSD) (i.e. ITQ) and secondary outcomes (depression, anxiety, alcohol use, and somatisation) (e.g. GHQ-12, AUDIT). Participants in both groups will be asked to complete these outcome measures at baseline, after 25-weeks post-treatment and then again after at a 12-week follow-up. The ITQ will be also completed by the ESTAIR group at the end of every module. In addition, data will be recorded on retention and DNA rate. The research assistant will be masked to group allocation to demonstrate to future funders this is achievable in a future trial.

**Note:** The ITQ will be completed by the therapist and participant at the end of every model. Due to feasibility concerns, the research assistant will not be masked to group allocation when collected measures at baseline, post-treatment, and follow-up. This is not expected to have any impact on outcomes as all primary and secondary outcome measures are self-report.

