### **Alcohol Use**

The presence of an Alcohol Use Disorder (AUD; Saunders et al., 1993) will be measured using the AUDIT-C, a brief self-report measure comprised of the first three questions of the *Alcohol Use Disorders Identification Test*. The clinical utility of the AUDIT-C has been demonstrated in multiple samples including the general population, military veterans, and hospitalised patients. Scores on the AUDIT-C range from 0-12, and based on a nationally representative sample of adults from the United States, scores  $\geq$  four effectively capture a DSM-5 diagnosis of AUD.

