#### ***Quantitative analyses***

The main analyses of the trial data will be conducted in 2 phases; (1) modelling within-subject changes in ITQ scores for data from the ESTAIR arm of the trial and a (2) comparison between the ITQ scores, and secondary outcome measures, for the ESTAIR and TAU groups at 25 weeks and 12 week follow-up.

Phase 1: An analogue to a repeated measures ANOVA will be specified as a structural equation model to handle missing data efficiently using robust maximum likelihood estimation (MLR: Schafer & Graham, 2002) and relax assumptions about the variance-covariance structure of the observations (Hoffman, 2015). An initial model will specify and estimate a model with the mean ITQ scores from the five observation periods (baseline, 7, 13, 19, 25 months) constrained to be equal, and then the model will be re-estimated with the means to be freely estimated. The difference in model fit can be tested using the loglikelihood difference test, which is distributed as a chi-square ( $\chi^2$ ). A significant  $\chi^2$  result indicates that the unconstrained model is better than the constrained model, meaning that the null hypothesis of equal means can be rejected (Hoffman, 2015). If this is the case pairwise differences in means will be tested using the Wald  $\chi^2$  test. The magnitude of the change in symptoms scores will be calculated using Cohen's  $d$  with a correction for repeated measures designs (dr). Values  $< 0.40$  reflect 'small' effects, values from 0.40 to 0.79 reflect 'medium' effects, and values  $> 0.80$  reflect 'large' effects.

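### Fitting five outcomes in one model does not remove the need to deal with multiple testing in the Phase 2 comparison

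*Combined protocol and SAP*

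**What the plan says.** The Phase 2 paragraph of the Quantitative analyses section opens: "The primary intention to treat analysis will be conducted to examine differences between the ESTAIR and TAU groups at 25 weeks". The method is a single model, "simultaneously regressing the 25 week mean scores of the ITQ, PHQ-9, GAD-7, PHQ-15, and AUDIT onto a dummy-coded binary variable". Each outcome has its own arm coefficient, and the p-value attached to each is to be read as showing statistical significance. The first of three reasons given for this approach is that "all the model parameters are estimated simultaneously thereby avoiding the need for post-hoc adjustment for multiple testing".

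Elsewhere the outcomes are ranked. The Study Design section describes the trial as "using the ITQ as the primary outcome". The Outcome Measures section speaks of the "acceptability of primary (PTSD and CPTSD) (i.e. ITQ) and secondary outcomes (depression, anxiety, alcohol use, and somatisation". The outline at the head of the Quantitative analyses section describes Phase 2 as a "comparison between the ITQ scores, and secondary outcome measures, for the ESTAIR and TAU groups at 25 weeks and 12 week follow-up".

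No alpha level or sidedness is given anywhere. The Sample size section states that no power calculation was possible and sets 30 participants per arm.

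**The concern.** Joint estimation is a way of fitting a model. It is not a procedure for controlling error across several tests. A reader who takes the Phase 2 paragraph at face value has five p-values under the heading of the primary analysis, permission to call any of them significant, and an assurance that no correction is needed. The ranking of the ITQ above the other scales, clear elsewhere, is not repeated there, and nothing in the paragraph says that the 25-week test is the ITQ coefficient.

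Phase 1 is handled differently. It starts with an overall test of equal means and only then moves on: "If this is the case pairwise differences in means will be tested using the Wald". Phase 2 has no such gate.

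The stake is how results are reported. Under the Progression Criteria section, the decision on a full trial depends on reaching target recruitment and on ITQ data from at least 75% of those randomised, so no p-value enters it. But the Study Design section presents this pilot as preparation for a larger trial with the same design parameters, and the same rationale would do more harm if carried over.

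**Working it through.** The plan gives no error rate, so there is no stated figure to reproduce.

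**Inputs from the plan.** Five outcomes in one model (Phase 2 paragraph); 30 per arm (Sample size section); robust maximum likelihood estimation (Phase 2 paragraph).

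**Assumed, because the plan is silent.** Two-sided 0.05 per test; a common correlation r between outcomes, varied from 0 to 0.9; no true difference on any outcome.

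**Step 1: does the joint fit change the tests?** Every equation has the same single predictor, trial arm. With complete data, the joint model therefore gives the same coefficients and standard errors as five separate regressions. A fit to one simulated dataset of 30 + 30 agreed to machine precision. The number of tests stays at five.

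**Step 2: at least one false positive among five.**

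- For r = 0: 1 − 0.95^5 = 1 − 0.7738 = 0.226.
- For r > 0, with c = 1.96: 1 − ∫ φ(u) [Φ((c − √r·u)/√(1−r)) − Φ((−c − √r·u)/√(1−r))]^5 du.

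**Step 3: a secondary scale is significant while the ITQ is not.** This is the any-of-five probability minus the 5% chance that the ITQ itself is significant. For r = 0: 22.6% − 5% = 17.6%.

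| r | Any of five, formula | Any of five, simulated t-tests | Any of five, simulated robust z | A secondary but not the ITQ (formula column − 5%) |
|---|---|---|---|---|
| 0 | 22.6% | 22.7% | 26.3% | 17.6% |
| 0.3 | 20.9% | 21.0% | 24.2% | 15.9% |
| 0.5 | 18.3% | 18.5% | 21.3% | 13.3% |
| 0.7 | 14.8% | 14.9% | 17.2% | 9.8% |
| 0.8 | 12.7% | 12.5% | 14.5% | 7.7% |
| 0.9 | 10.2% | 10.3% | 12.0% | 5.2% |

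The simulations used 30 per arm and 40,000 replicates. The ITQ tested alone gave 4.8% to 5.2% with t-tests and about 6% with robust z. The excess of the robust-z column over the t column comes from using a normal reference in a small sample and is not a multiplicity effect.

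**Step 4: missing data.** With uneven missingness the joint and separate fits are no longer identical. The check assumed 60 randomised, 15% lost entirely and a further 12% lost independently per outcome, so ITQ completeness is 0.85 × 0.88 = 74.8%. It used 2,500 replicates (Monte Carlo standard error up to 0.9 percentage points). With robust z, any of five was significant in 28.5% (r = 0), 22.8% (0.5) and 12.9% (0.9) of joint fits, against 27.8%, 22.6% and 16.5% for separate fits. The joint fit does better at high correlation, but it does not control the error.

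**The case against.** The strongest reply is that the five outcomes are not co-primary. The Study Design and Outcome Measures sections make the ITQ primary, and the Phase 2 outline calls the other scales secondary. In the Phase 2 paragraph, the word primary may refer only to the 25-week time point, as against the 12-week follow-up, and to the intention-to-treat set. On that reading the 10% to 23% range does not describe the primary analysis at all. This stands as a limit on the size of the problem, and the range is given here only conditionally. It does not rescue the stated reason, which is false on either reading, and it leaves the Phase 2 paragraph without a named primary test.

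A second reply is that this is a pilot: none of its four research questions concerns efficacy, and progression uses no p-value. That is right and keeps the consequence small. A pilot may leave secondary outcomes unadjusted if it labels them so. Here they sit under a primary label with a faulty justification.

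Third, the section on the ITQ describes clusters and diagnoses but no total score. The analysis text treats the ITQ as one score, and the statement that an ITQ-only test is not inflated by multiplicity assumes that. If two ITQ scores were tested, the chance of a false positive on either would be 9.8% (r = 0), 9.1% (0.5) or 7.0% (0.9). The score should therefore be named.

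Finally, the missingness pattern in Step 4 is assumed, and its figures mix multiplicity with small-sample inflation. They serve only to show that missing data do not make the plan's reason true.

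**Conclusion.** The concern holds. Simultaneous estimation does not avoid the need to deal with multiple testing, and Phase 2 offers nothing else that does.

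- **ITQ as the single primary test:** no inflation from multiplicity. The rate is 5% with a t reference and about 6% with robust z; the extra point is a separate small-sample matter.
- **All five read as primary:** familywise error of about 23% at correlation 0, falling to 10% at 0.9.
- **Reporting risk in either case:** with no true effect, the chance that some secondary scale is significant while the ITQ is not runs from about 18% (r = 0) through 13% (0.5) to 5% (0.9).

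These figures rest on two-sided 0.05 and an equal correlation between outcomes, neither of which the documents supply. The progression decision is unaffected. This should be fixed, because the statement is plainly wrong and correcting it costs almost nothing.

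**What to change.** In the Phase 2 paragraph:

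1. Delete the first reason, on simultaneous estimation and multiple testing.
2. State a two-sided alpha of 0.05.
3. Define the primary between-group test as the arm coefficient for the ITQ at 25 weeks, naming the ITQ score used.
4. Label PHQ-9, GAD-7, PHQ-15 and the alcohol measure at 25 weeks, and every 12-week follow-up comparison, as secondary. Report them as estimates with 95% confidence intervals and make no significance claims.
5. Use one name for the alcohol measure. The Outcome Measures list and the Phase 2 paragraph say AUDIT, while the Alcohol Use section says it "will be measured using the AUDIT-C, a brief self-report measure comprised of the first three questions".

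That is enough for a pilot. If p-values are to be kept for the four secondary scales at 25 weeks, one option is to test them with Holm's procedure only after a significant ITQ test, using a t reference. When nothing differs, the familywise error is then about 5% (about 6% with robust z).

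The cost is a change of wording. No data, visits or sample size are affected. The only thing given up is the ability to declare secondary results significant without adjustment.

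### The Phase 2 arm-only regression is a complete-case analysis for anyone who misses the whole 25-week assessment, so robust maximum likelihood does not use all available data for them

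*Combined protocol and SAP*

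**What the plan says.** Under Data analysis, Quantitative analyses, Phase 2: "The primary intention to treat analysis will be conducted to examine differences between the ESTAIR and TAU groups at 25 weeks". The method is given as "simultaneously regressing the 25 week mean scores of the ITQ, PHQ-9, GAD-7, PHQ-15, and AUDIT onto a dummy-coded binary variable", coded ESTAIR = 1 and TAU = 0, and "The estimated regression coefficient for each variable indicates the mean difference between the treatment and control group". No baseline score, follow-up score, module-end score or auxiliary variable is named. The second of three reasons for this approach is that "the use of robust maximum likelihood (MLR) estimation allows for missing data to be handled efficiently by using all available data".

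More data than that are collected. Under Outcome Measures: "Participants in both groups will be asked to complete these outcome measures at baseline, after 25-weeks post-treatment", and again at the 12-week follow-up. In addition, "The ITQ will be also completed by the ESTAIR group at the end of every module". The opening of Quantitative analyses describes Phase 2 as a "comparison between the ITQ scores, and secondary outcome measures, for the ESTAIR and TAU groups at 25 weeks and 12 week follow-up", but the Phase 2 paragraph specifies a model for 25 weeks only.

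Progression Criteria for a Full Trial requires 25-week ITQ data from at least 75% of those randomised. The plan states no missing-data assumption for Phase 2 and no sensitivity analysis.

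**The concern.** Maximum likelihood can draw on a participant with missing data only through other variables of that participant in the same model. Here all the outcomes come from one contact, so a missed contact removes the participant entirely. The stated reason therefore promises protection that the model cannot give for whole-visit loss, which is the kind of loss that the progression rule counts.

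If ESTAIR participants who are doing badly are more often missing at 25 weeks, and TAU participants are not, the reported effect flatters ESTAIR. The plan will report p-values and effect sizes from this model, and Sample size says that the pilot will enable the sample size of a full trial to be calculated. An inflated effect, if used there, would make that trial too small.

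**Working it through.** **Inputs from the documents.** 30 per arm, 60 in total (Sample size). At least 75% with 25-week ITQ: 0.75 x 60 = 45, so up to 15 may be missing, with no split by arm. The documents give no correlations, dropout pattern, SD or effect size, so everything below on size rests on assumptions. There is no figure of the plan's own to reproduce.

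**Step 1: what the model does with an absentee.** The log-likelihood is the sum over participants of log f(observed 25-week scores | arm). If all five scores are missing, that participant's term is log 1 = 0. The estimates are then those from attenders alone. Numerical check: 60 simulated participants, 15 with all five scores missing. The full-information maximum likelihood arm coefficients for all 60 were -0.15968, -0.27892, 0.18905, -0.23953 and -0.07163. Ordinary regression on the 45 attenders gave the same values (largest difference below 1e-15).

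**Step 2: where the plan's statement is true.** When three attending ESTAIR participants lacked only the ITQ, the ITQ coefficient was -0.188 by maximum likelihood and -0.194 from complete cases. Their other questionnaires do contribute.

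**Step 3: size under strict selection.** Take SD 1, a true difference of 0, and TAU loss nil or random. Suppose the worst fraction p of ESTAIR on the last module-end ITQ miss week 25, and that this score correlates r with the 25-week ITQ. Then bias = -r x φ(z)/(1-p), where z is the standard normal (1-p) quantile.
- p = 0.25: z = 0.674, φ(z) = 0.318 and 0.318/0.75 = 0.424. With r = 0.8 the bias is -0.34.
- At the same p, r = 0.6 gives -0.25 and r = 0.9 gives -0.38.
- With r = 0.8, p = 0.10 gives -0.16. If all 15 tolerated losses fall in ESTAIR, p = 15/30 = 0.50 and the bias is -0.64.

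**Step 4: softer selection.** With r = 0.8, 25% ESTAIR loss and log-odds of loss rising by 0.5 to 1 per SD of the module-end ITQ, simulated bias is -0.10 to -0.18. At 30 per arm, with log-odds 1, type I error is about 9% against a nominal 5%. With loss unrelated to response, bias is about 0 and type I error about 5%.

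**Step 5: what added data recover.** A second simulation used 30 per arm, a true effect of -0.5 SD, about 30% ESTAIR loss (log-odds 1.0 to 1.5 per SD of mid-treatment ITQ) and 20% random TAU loss. Correlations were 0.5 (baseline with week 25), 0.7 (mid-treatment with week 25) and 0.7 (week 25 with follow-up), and 30% of week-25 absentees were seen at follow-up.

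| Analysis | Bias (SD) |
|---|---|
| As planned | -0.19 to -0.27 |
| Complete cases, baseline-adjusted | -0.12 to -0.18 |
| Joint baseline, 25 weeks, follow-up | -0.09 to -0.15 |
| Joint model plus the mid-treatment ITQ at its own fixed time | 0.00 to -0.02 |

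With 25% missing completely at random, none is biased. The SD of the estimate is 0.305 as planned, 0.268 baseline-adjusted and 0.254 in the joint model; (0.254/0.305)^2 = 0.69, so variance falls by about 31%.

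**Step 6: how the module-end ITQ enters matters.** The near-zero last row of the table needs a score at a fixed time. A single last-available score is a late one for completers and an early one for those lost. ESTAIR arm simulated with 30% loss after modules 1 to 3, linear improvement and six-week autocorrelation 0.8 to 0.9:
- Loss unrelated to response: the plan has bias 0.00. The last-available score gives +0.07, +0.13 and +0.20 SD (against ESTAIR) for improvements of 0.5, 1.0 and 1.5 SD.
- Loss rising with current ITQ, improvement 1.0 SD: the plan gives -0.18 to -0.29 and the last-available score +0.18 to +0.24.
- Module-end scores entered separately at their own times give about 0.00.

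**Step 7: loss that depends on the unseen 25-week score.** At 25% ESTAIR loss under strict selection, the plan has bias -0.42. Adding baseline and module-end ITQ leaves -0.13 to -0.32, so bias shrinks but remains.

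**The case against.** Several points on the other side stand.

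- Leaving ESTAIR is not the same as missing week 25. A reader might infer that dropout from therapy alone biases the comparison. The Procedure section has the research assistant contact participants at 25 weeks with no condition on attendance at therapy. The withdrawal section mentions only feasibility use of withdrawn participants' data and does not say whether they are still assessed. The documents leave this open, so the bias is conditional.
- A reader might also infer that the analysis is not intention to treat. The text does not support that: participants are compared as randomised, and nothing in Phase 2 excludes those who did not complete therapy. The fair criticism is an unstated missing-data assumption.
- The stated reason is not simply false, since it holds for partial non-response at an attended visit.
- Similar selection in both arms would largely cancel. The scenarios above put selection in ESTAIR only, and no figure in the documents supports that choice.
- At 30 per arm the random error (SD 0.305) exceeds most of the biases shown. That limits what one pilot estimate can mislead about, but it does not make the bias harmless: the bias has a direction and raises type I error.
- The research questions concern recruitment, retention and acceptability, and progression does not use the effect estimate. Sample size also does not say that the between-arm effect will be the input to the full trial. This lowers the severity without removing the point.

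**Conclusion.** The point holds in a limited form. For whole-visit loss at 25 weeks, the planned model is exactly a complete-case analysis, and the claim about available data applies only to partial non-response. This follows from the model as written and needs no assumption.

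Bias arises only if loss of the 25-week assessment is related to response and differs by arm. With about 25 to 30% ESTAIR loss related to earlier ITQ, and TAU loss random or nil, it is about -0.1 to -0.35 SD in favour of ESTAIR (up to -0.38 under strict selection with a correlation of 0.9). It is zero if loss is unrelated to response. These sizes are illustrative.

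Two stronger conclusions should be resisted. Baseline adjustment alone does not cure the problem. Nor does the problem block a feasibility pilot: it should be fixed, but the progression decision does not depend on it.

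**What to change.** 1. Replace the arm-only regression with one robust maximum likelihood model per measure. Model baseline, 25-week and 12-week follow-up scores jointly, with free covariances, a common baseline mean and arm-specific means at 25 weeks and follow-up. Report the arm difference at both occasions. This uses the baseline and follow-up scores of absentees, improves precision and supplies the follow-up comparison already promised. It removes only part of the bias.
2. For the ITQ, enter the module-end scores as separate variables at their own time points. They exist only in ESTAIR, so state the ESTAIR-only covariance structure. Do not use a single last-available score, which acts like carrying an early score forward and creates bias of its own.
3. Limit the second stated reason to questionnaires missing from an attended visit, and state the missing-at-random assumption.
4. Keep the complete-case result as a comparison, and add a sensitivity analysis for loss that depends on the unseen 25-week score.

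The cost is analysis-plan wording and a larger model with the same estimator, using data already being collected. The downside is a heavier model at 30 per arm, which may not converge with all module scores included.
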